### **1. Justification / context**

In France, Alzheimer's disease accounts for 70 to 80% of the causes of neurocognitive disorders, i.e. 600,000 to 800,000 patients. It is a neurodegenerative pathology that causes evolutionary cognitive dysfunction, mainly affecting memory functions. The inability to name familiar objects (lack of the word) is one of the most commonly noted symptoms at an early stage of the disease.

Presbycusis, or age-related hearing loss, is the most common sensory deficit in the elderly which is manifested socially by a progressive discomfort of verbal communication. Presbycusis remains underdiagnosed and undertreated: 2/3 of the patients are not using hearing aid.

In recent years, a link between neurocognitive disorders and hearing loss has been shown by investigating general cognition. In this study, we are investigating lexical disorders.

### **2. Objectives**

#### **2.1. Main objective**

To determine the relationship between word loss and presbycusis suspected or proven in patients with Alzheimer's disease or related disorders.

#### **2.2. Secondary objective**

Study variables associated with word loss in patients with Alzheimer's disease or related disorders.

### **3. Outcome measures**

#### **3.1. Primary outcome measure**

The lack of word score (BIMM questionnaire) according to the score at the hearing questionnaire.

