#### **3.2. Secondary outcome measure**

Age, gender, socio-cultural level, accommodation, laterality, main diagnosis, hearing aid, speech language therapy according to lack of word score.

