### **7.2. Conducting the visit**

Study participants will benefit from an additional speech therapy consultation of approximately one hour. During this visit, they will pass the lack of word questionnaire (BIMM noun and verb naming tests) and complete the hearing questionnaire.

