## **10. Statistical aspects**

The parameters collected will be presented in tables with descriptive statistics for the entire study population and sub-populations (patients with hearing impairment and patients without hearing impairment).

The correlation study between the overall score obtained at the lack of word questionnaire and the score obtained at the hearing questionnaire will be presented in a scatter plot and the Pearson correlation coefficient will be calculated.

The study of the relationship between factors and word deficiency in patients with Alzheimer's disease or related disorders will be carried out by bivariate analysis and then by logistic regression.

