## **12. Expected benefits**

If this study does show a link between presbycusis and lexical disorders in patients with Alzheimer's disease or related disorders, a new study will be required in a larger, multicentre population to confirm the results.

Prevention and management of patients with Alzheimer's disease or related disorders could be improved. Indeed, systematic screening for hearing disorders could be considered as soon as Alzheimer's or related diseases are suspected. In addition, in these patients, speech and language therapy management may evolve to include two areas: management of language and memory disorders, and management of hearing disorders.

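### Does the plan's silence on aided or unaided answers to the hearing questionnaire call for a change to the primary correlation or to its conclusion?

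*Combined protocol and SAP*

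**What the plan says.** The main objective (Section 2.1) is "To determine the relationship between word loss and presbycusis suspected or proven in patients with Alzheimer's disease or related disorders". The primary outcome (Section 3.1) is "The lack of word score (BIMM questionnaire) according to the score at the hearing questionnaire". At the single visit of about one hour (Section 7.2), patients take two tests: "they will pass the lack of word questionnaire (BIMM noun and verb naming tests) and complete the hearing questionnaire". No audiometry or ear examination is listed, the questionnaire is not named, and no instruction to hearing-aid users is given.

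For the primary analysis, Section 10 states that the word score and "the score obtained at the hearing questionnaire will be presented in a scatter plot and the Pearson correlation coefficient will be calculated". There is no adjustment or stratification.

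Hearing-aid use is among the secondary variables in Section 3.2: "Age, gender, socio-cultural level, accommodation, laterality, main diagnosis, hearing aid, speech language therapy according to lack of word score". Section 10 also presents all collected parameters in descriptive tables, for the whole sample and separately for patients with and without hearing impairment. It then examines factors related to word deficiency by bivariate analysis and logistic regression.

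Section 12, on expected benefits, begins "If this study does show a link between presbycusis and lexical disorders in patients with Alzheimer's disease or related disorders" and continues that a larger multicentre study would be needed to confirm the result.

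**The concern.** Two things look wrong on a first reading. First, the exposure is named as presbycusis but measured only by questionnaire. No step confirms a loss or attributes it to age, yet Section 12 speaks of a link with presbycusis.

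Second, a hearing aid can change the answers. A patient with marked loss and a good aid may report little difficulty. If the intended exposure is unaided loss, such a patient sits at the wrong place on the horizontal axis and pulls the correlation towards zero. Hearing-aid use is recorded but does not enter the primary correlation. A weak coefficient could then mean either no association or mixed answering, and a reader of an unmarked scatter plot could not tell which. A follow-up study planned on that coefficient would inherit the ambiguity.

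**Working it through.** **The plan's own figure.** 10 patients per month × 5 months = 50, which agrees with the recruitment potential in Section 8. The planned 45 is 45/50 = 90% of it, with no refusal rate stated. There is no power calculation or expected correlation, so every input below is an assumption.

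**Precision at n = 45.** Take r = 0.40 and Fisher's z: atanh(0.40) = 0.424 and 1.96/√(45 − 3) = 0.302. The 95% interval is tanh(0.424 ± 0.302) = 0.12 to 0.62. With two-sided alpha 0.05, approximate power is Φ(0.424 × √42 − 1.96) = 78%.

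**Possible dilution.** Assumptions:
- The true correlation of naming deficit with unaided loss is 0.40. This builds the dilution in.
- 50–70% of patients are impaired, and 10% to one third of these are aided. One third is the complement of the background statement in Section 1 that "2/3 of the patients are not using hearing aid"; it is not a figure for this cohort.
- Half correction moves an aided score halfway to the unimpaired mean. Full correction redraws it from the unimpaired patients.
- Aids go to impaired patients at random, with probability rising with severity, or to the worst affected.

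Simulated results for 60% impaired and one third of them aided (r from two million draws; share with p < 0.05 from 20,000 samples of 45):

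| Who is aided | r, half | r, full | r, aided excluded | p < 0.05: half / full / excluded |
|---|---|---|---|---|
| Random | 0.373 | 0.286 | 0.401 | 73% / 48% / 70% |
| Rising with severity | 0.363 | 0.228 | 0.366 | 71% / 33% / 62% |
| Worst affected | 0.354 | 0.152 | 0.314 | 68% / 19% / 49% |

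Without distortion the share is 79%. Over all the prevalences and aid rates above, r is 0.34–0.39 under half correction and 0.10–0.37 under full correction. It stays at 0.40 if aids do not change the answers. If naming follows aided hearing, it is also 0.40 (checked for one third aided at random with full correction). The middle row depends on how severity is weighted: another coding gave 0.18–0.24 under full correction with one third aided, against 0.20–0.25 here.

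**Would excluding aided patients help?** The expected loss is 45 × 0.60 × 1/3 = 9, leaving 36. The interval at r = 0.40 becomes tanh(0.424 ± 1.96/√33) = 0.08 to 0.64. Under half correction, exclusion lowers the chance of p < 0.05 in every row. With the worst affected aided, it also moves r from 0.354 to 0.314, further from 0.40, because it narrows the range of hearing scores. Under full correction it does recover part of the loss.

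The data could not show which case applies. Excluded minus primary r, with its 95% sampling range:
- No distortion: −0.14 to 0.13 (random), −0.30 to 0.14 (worst aided).
- Half correction: −0.04 to 0.11 (random), −0.14 to 0.06 (worst aided).
- Full correction: −0.01 to 0.30 (random), 0.01 to 0.36 (worst aided).

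A difference of 0.10, for example, fits no distortion under either pattern, full correction under either pattern, and half correction with aids at random.

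**The wording.** Section 2.1 includes suspected presbycusis, which a questionnaire can support. Section 12 is a conditional statement of possible benefit, not a rule for reporting, and it requires confirmation.

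**Use of hearing-aid status.** It is a collected variable, so the Section 10 tables show it by hearing-impairment group. If those groups are formed from the questionnaire (their source is not stated), well-corrected aid users would appear in the unimpaired column.

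**The case for a change.** The strongest case for a change is that the silence is real and cheap to end. Without an aided or unaided basis, a reader cannot say exactly what the hearing score measures. The logistic regression does not help, because it relates hearing-aid use to word deficiency and does not make hearing scores comparable between users and non-users. The hearing-impairment groups have no stated definition, so the table is not a sure safeguard. Section 12 drops the word suspected and goes on to systematic hearing screening and changes in speech therapy. One sentence and a second plotting symbol would cost no patients and no power.

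Most of that is fair as description. It is good practice to give all patients the same instruction, to mark aid users on the plot, and to report the exposure as questionnaire-reported hearing difficulty. But these steps record how the questionnaire was given and how the result is labelled. They leave the primary estimate, sample and method as they are. The questionnaire is not in the documents and may carry its own instruction. The only substantive analytic change on offer, the correlation without aided patients, has no clear gain on the figures above.

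**Conclusion.** No change to the plan follows. The gap is genuine but small, and a competent analyst fills it when giving the questionnaire and drawing the planned scatter plot. Whether it affects the correlation at all cannot be determined from the documents. Under the stated assumptions, the effect on a true 0.40 runs from nothing to a fall to 0.10. The low end needs the most severely affected to be aided and also to score like unimpaired patients. Under half correction the coefficient stays at 0.34–0.39, small beside a 95% interval of 0.12 to 0.62 at n = 45.

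Excluding aided patients would cost about 9 of 45, and its result could not be told from chance. The presbycusis label is a matter of interpretation in a single-centre case series whose objective includes suspected cases and whose findings the protocol itself says need confirmation. The judgement would differ if the questionnaire were shown to mix aided and unaided answers and most severe cases were well corrected; the documents show neither.

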#### **3.2. Secondary outcome measure**

Age, gender, socio-cultural level, accommodation, laterality, main diagnosis, hearing aid, speech language therapy according to lack of word score.

### **4. Outline of the research**

Monocentric study on a series of cases.

### **5. Eligibility criteria**

#### **5.1. Inclusion criteria**

- > 65 years old
- French mother tongue
- Good vision with or without correction
- Alzheimer's or related disease (15 <Mini-Mental State Examination<25)
- Affiliate or beneficiary of a social security
- Informed consent

#### **5.2. Exclusion criteria**

- Cognitive disorders related to another pathology (cerebrovascular accident, head trauma, epilepsy ...)
- Protected patient (under guardianship) or person deprived of liberty by judicial or administrative decision

## **6. Feasibility and recruitment procedures**

Recruitment will take place in the various departments of the Centre de Soins pour Personnes Agées (CSPA): geriatric day hospital, long-term care units, follow-up care and rehabilitation units.

## **7. Research procedures**

### **7.1. Consent**

During the inclusion visit, the doctor, neuropsychologist or speech-language pathologist informs the participant and answers all questions about the objective, the nature of the constraints, and the expected benefits of the research. It also specifies the participant's rights in a research project and checks the eligibility criteria. The patient gives his or her consent orally or in writing, which is documented in the medical file.

### **7.2. Conducting the visit**

Study participants will benefit from an additional speech therapy consultation of approximately one hour. During this visit, they will pass the lack of word questionnaire (BIMM noun and verb naming tests) and complete the hearing questionnaire.

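### The hearing score comes from patients with MMSE 16 to 24 and is correlated with naming without using MMSE, so disease stage can mask or inflate the primary correlation undetected

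*Combined protocol and SAP*

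**What the plan says.** - **Exposure.** At one visit of about an hour, section 7.2 says of participants that "they will pass the lack of word questionnaire (BIMM noun and verb naming tests) and complete the hearing questionnaire". The protocol does not name or describe the hearing questionnaire. It mentions no audiometry, carer version or measure of awareness.
- **Primary outcome (section 3.1).** "The lack of word score (BIMM questionnaire) according to the score at the hearing questionnaire". The questionnaire score is the only hearing measure in it.
- **Target (section 2.1).** "To determine the relationship between word loss and presbycusis suspected or proven". No procedure for establishing proven presbycusis is given.
- **Population (section 5.1).** "Alzheimer's or related disease (15 <Mini-Mental State Examination<25", that is, integer scores 16 to 24.
- **Primary analysis (section 10).** The two scores "will be presented in a scatter plot and the Pearson correlation coefficient will be calculated". No covariate is mentioned.
- **Secondary analysis.** Section 3.2 lists the factors: "Age, gender, socio-cultural level, accommodation, laterality, main diagnosis, hearing aid, speech language therapy according to lack of word score". Their relation to word deficiency "will be carried out by bivariate analysis and then by logistic regression". MMSE is not listed, and this analysis would not adjust the Pearson coefficient in any case.
- **Descriptive groups (section 10).** "patients with hearing impairment and patients without hearing impairment", without a stated definition.

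**The concern.** Stage of disease may act on both axes of the primary scatter plot. Section 1 describes a progressive disease that mainly affects memory, with word-finding difficulty as a common early sign, so naming is likely to vary across MMSE 16 to 24. The hearing score depends on what the patient recalls and notices about everyday hearing, and that may also vary with stage. Purely random reporting error would only weaken a correlation. An error that moves with stage adds a component of its own, which can cancel the hearing-naming link or add to it.

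The plan has no display or estimate that would show this, although eligibility requires an MMSE score. The main result could be misread in either direction. Section 12 makes a larger multicentre study follow if a link is shown, so a masked link and a spurious one both matter. Groups formed from the hearing score would carry the same distortion.

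**Working it through.** **The plan's own figure.** Sections 8 and 9: 10 patients per month x 5 months = 50, matching the stated recruitment potential. The planned 45 is 45/50 = 90% of that. No alpha, power or target correlation is given, so 45 cannot be reproduced as a statistical sample size. Below I assume a two-sided alpha of 0.05 and the Fisher z approximation.

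**Model (every path value is an assumption).** All variables are standardised within the enrolled range. H is true hearing difficulty, M is entry MMSE, N is naming performance and R is reported hearing difficulty. A negative r is the hypothesised link.

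- N = -0.3 H + 0.5 M + error, with var(N) = 1
- R = H + a M, where a is the under-reporting per SD of worsening stage

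**Case 1: H unrelated to M.** Crude r = (-0.3 + 0.5a) / sqrt(1 + a²). The MMSE-adjusted value is -0.3 / sqrt(1 - 0.5²) = -0.35 for every a.

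| a | crude r | power, n = 45 |
|---|---|---|
| 0 | -0.30 | 52% |
| 0.2 | -0.200/1.020 = -0.20 | 25% |
| 0.4 | -0.100/1.077 = -0.09 | 9% |
| 0.6 | 0/1.166 = 0.00 | 5% |

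The crude |r| must exceed tanh(1.96/sqrt(42)) = 0.29 to be significant.

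With a weaker stage-naming path of 0.3, crude r = (-0.3 + 0.3a)/sqrt(1 + a²) = -0.24, -0.17 and -0.10 at a = 0.2, 0.4 and 0.6. The adjusted value is -0.3/sqrt(0.91) = -0.31. The masking is smaller but in the same direction.

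**Case 2: true hearing difficulty rises as MMSE falls, corr(H, M) = -0.3, other paths as in case 1.** Here cov(H, N) = -0.3 - 0.15 = -0.45 and cov(M, N) = 0.5 + 0.09 = 0.59. Crude r = (-0.45 + 0.59a) / sqrt(1 + a² - 0.6a). The adjusted value is -0.3 sqrt(0.91) / sqrt(1 - 0.59²) = -0.35.

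| a | crude r | against -0.35 adjusted |
|---|---|---|
| 0 | -0.45 | inflated |
| 0.2 | -0.332/0.959 = -0.35 | about equal |
| 0.4 | -0.214/0.959 = -0.22 | masked |
| 0.6 | -0.096/1.000 = -0.10 | masked |

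The sign of the net bias therefore depends on quantities that the documents do not give.

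**Which check would work?**

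- *Correlation of hearing score with MMSE.* In case 2 at a = 0.4 it is (a - 0.3)/0.959 = 0.10, although crude r has moved from -0.45 to -0.22. With 45 patients 0.10 cannot be told from zero, so it is useful as description but not as a trigger.
- *Splitting MMSE into two bands.* Stage still varies within a band. In case 1 at a = 0.6, with normally distributed stage split at the median, the variance of M within a half is 1 - 2/π = 0.363. The within-band r is (-0.3 + 0.3 x 0.363)/sqrt(1.131 x 0.841) = -0.20, not -0.35. With about 22 patients in a band, the 95% interval for an r of magnitude 0.35 runs from about -0.08 to 0.67.
- *Partial correlation on continuous MMSE.* It recovers -0.35 in both cases. With 45 patients and one covariate, SE(z) = 1/sqrt(41) = 0.156. The 95% interval around -0.35 is then roughly -0.58 to -0.05.

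**The case against.** A reader might infer that awareness of hearing is known to fall with stage, so that the study is biased towards finding nothing. The documents do not support that. Section 1 speaks of memory, not of insight into hearing, and no figure for under-reporting appears anywhere. Section 1 also reports a link between hearing loss and general cognition. That sits badly with treating hearing as independent of stage, and case 2 shows that the bias can then run the other way. Masking is a possibility, not a finding.

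The questionnaire is also undescribed, and a therapist may read out the items. That stands, but help with a form still leaves the patient as the source of the answers.

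Finally, this is a single-centre case series meant to generate a hypothesis. Section 12 says what follows if a link is shown and states no rule for a null result, so it would go too far to say that a null ends the programme. This limits the stakes. It does not remove the case for an estimate that needs no new assessment.

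**Conclusion.** The concern holds in this form: the primary coefficient mixes any hearing-naming link with whatever stage does to both scores, and nothing in the plan would show it. Under assumed paths with hearing unrelated to stage, crude r falls from -0.30 to between -0.20 and 0.00, against about -0.35 after adjustment. With an assumed hearing-MMSE correlation of -0.3, crude r ranges from -0.45 (inflated) to -0.10 (masked) around the same adjusted value. These figures show that the effect could matter with 45 patients. They do not estimate its size in this study. The exact recovery of the adjusted value depends on a linear shift with stage, MMSE standing in for stage, and a hearing score otherwise free of error.

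**What to change.** In section 10:

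1. Keep the crude Pearson coefficient. Beside it, report the partial correlation of BIMM score and hearing score adjusted for continuous entry MMSE, with a 95% confidence interval, in all patients with both scores.
2. Mark MMSE on the scatter plot, and report the hearing-MMSE correlation as description. Displays by MMSE band are optional and descriptive only.
3. State that a null crude correlation will not be read as no link without the adjusted estimate and its interval.
4. State as a limitation that adjustment removes a linear stage shift but does not show that the self-report is valid at every stage.

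The cost is one extra estimate and a marked plot, from a score that eligibility already requires. That score should be kept as a number in the case report form. The downside is that, if stage lies on the pathway between hearing and naming, adjustment may remove part of the association of interest, which is why both estimates should be shown.

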### **7.3. Rules for stopping a person from participating in the research**

At any time, if desired, the patient may withdraw from the study. He will continue to receive the best possible medical care.

Discontinuations from research will be patients for whom evaluations have not been completed. These patients will not be replaced.

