## **8. Study size**

Expected new entries are of 10 patients per month at the Centre de Soins pour Personnes Agées. The recruitment potential is 50 patients over the duration of the study.

Taking into account possible refusals to participate, patient availability and service organization, we plan to enroll 45 patients.

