### **11.2. Source data**

All information contained in original documents, or in authenticated copies of these documents, relating to clinical examinations, observations or other activities conducted as part of a research study and necessary for the reconstitution and evaluation of the research. The documents in which the source data are saved are called the source documents.

The data that will be entered directly into the case report form and that will not have any source data as a result are all the scores and reaction times obtained in the lack of word and hearing questionnaires.

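### Does the plan need a rule for patients whose naming or hearing assessment is left incomplete?

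*Combined protocol and SAP*

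**What the plan says.** All assessments take place in one visit of about an hour, at which, under Section 7.2, "they will pass the lack of word questionnaire (BIMM noun and verb naming tests) and complete the hearing questionnaire". Section 7.3 allows withdrawal at any time ("At any time, if desired, the patient may withdraw from the study"), defines discontinuation as incomplete evaluation ("Discontinuations from research will be patients for whom evaluations have not been completed") and adds "These patients will not be replaced". Section 8 sets the size: "we plan to enroll 45 patients".

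Section 10 promises "descriptive statistics for the entire study population and sub-populations (patients with hearing impairment and patients without hearing impairment"), and names the primary analysis: "The correlation study between the overall score obtained at the lack of word questionnaire and the score obtained at the hearing questionnaire", shown as a scatter plot with a Pearson coefficient. It names no analysis set, gives no missing-data rule and does not say how a half-finished BIMM is scored.

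Section 11.2 lists the items that go straight onto the case report form and "that will not have any source data as a result are all the scores and reaction times obtained" in the two questionnaires.

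**The concern.** The protocol expects some incomplete assessments, since it defines them and declines to replace them, yet the statistical section does not mention them. A patient without a hearing score belongs to neither hearing subgroup in the tables. A patient with only one naming test has no obvious overall score.

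The loss might not be random. Patients have MMSE between 15 and 25 and face about an hour of naming tests and a hearing questionnaire. Poor naming or poor hearing could each make it harder to finish, and these are the two variables being correlated. If completion depends on both, the complete-case coefficient is biased. The bias is towards zero when the true link is positive and the worst patients on both are lost, and upwards when poor namers with good hearing are lost. Because the scores have no source document behind the case report form, a partial result never written down could not be rebuilt later. That would make the omission a matter to settle before data collection.

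**Working it through.** **The plan's own figures.** Section 8 gives 10 entries per month and Section 9 gives 5 months: 10 × 5 = 50, the stated potential. The step to 45 (45/50 = 90%) is a judgement covering refusals, availability and organisation. There is no completion rate, expected correlation or power, so everything below rests on assumptions.

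**Assumptions.** 5 or 9 of 45 incomplete (5/45 = 11%, 9/45 = 20%), leaving n = 40 or 36. True correlation 0.40 or 0. Both scores are coded so that higher is worse.

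**Precision.** The 95% interval is tanh(atanh(r) ± 1.96/√(n−3)), with atanh(0.40) = 0.4236.

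| n | 1.96/√(n−3) | 95% CI at r = 0.40 |
|---|---|---|
| 45 | 0.302 | 0.12 to 0.62 |
| 40 | 0.322 | 0.10 to 0.63 |
| 36 | 0.341 | 0.08 to 0.64 |

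Not replacing patients costs little.

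**Bias, graded loss.** Hearing, noun and verb scores are trivariate normal, with overall = noun + verb and a noun–verb correlation of 0.7. Non-completion is logistic with slope 1 per standard deviation, calibrated to 11% or 20%, with 1 million draws per cell. Complete-case r:

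| Loss depends on | True 0.40: 11% / 20% | True 0: 11% / 20% |
|---|---|---|
| Nothing (random) | 0.40 / 0.40 | 0.00 / 0.00 |
| Hearing only | 0.388 / 0.381 | 0.00 / 0.00 |
| Noun naming only | 0.390 / 0.384 | 0.00 / 0.00 |
| Poor hearing and poor overall naming | 0.334 / 0.300 | −0.064 / −0.095 |
| Poor noun naming with good hearing | 0.434 / 0.450 | +0.058 / +0.086 |

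Loss tied to one score moves r by about 0.01 to 0.02. Loss tied to both moves it by at most 0.40 − 0.30 = 0.10. The half-width of the n = 45 interval is (0.62 − 0.12)/2 = 0.25.

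**Bias, extreme loss.** If the worst 10% or 20% on naming and hearing combined are removed by a sharp cut-off, an assumed true correlation of size 0.30 shrinks to 0.14 or 0.04. The larger shift, 0.30 − 0.04 = 0.26, approaches the half-width at n = 36, where the interval around 0.30 is −0.03 to 0.57: (0.57 + 0.03)/2 = 0.30. This is deliberately severe, and nothing in the documents suggests it.

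**Would a written rule change the primary result?** The coefficient needs a pair of scores per patient. A rule limiting the primary set to patients with both scores describes what the calculation already does.

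**Are partial scores lost?** Section 11.2 makes the case report form the original record. It does not say that completed parts of an unfinished visit go unrecorded. The form itself is not among the documents, so its fields cannot be presumed absent.

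**The case for a change.** The strongest case for a change is that partial scores can repair the estimate. If patients who stop during the verb test keep their noun and hearing scores, maximum likelihood on all recorded scores gives 0.38 to 0.40 when the true value is 0.40. At n = 45 with 20% lost on hearing and overall naming, its root mean square error is 0.133, against 0.186 for complete-case and 0.126 with full data. The cost would be a few form fields and a sentence or two in Section 10.

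The arithmetic stands, but its reach is narrow. It assumes the verb test is the part that goes missing, whereas Section 7.2 fixes no order of tests. The recovery occurs because the noun test stands in for the verb test. If instead the hearing score or the whole BIMM is missing, and loss depends on both hearing and naming, likelihood gives 0.35 / 0.32 (11% / 20% lost) in either case, little better than complete-case at 0.33 / 0.30. Recording more therefore does not guarantee a correction. Where partial scores have been entered, nothing in the plan prevents an analyst from using them in a supporting analysis.

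It is also fair to say that readers need the number analysed, the number incomplete and the reasons. Any competent report gives these without a protocol instruction.

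**Conclusion.** The silence is real, but it is missing detail that analysts fill sensibly, not an error in the plan. The primary coefficient is complete-case whether or not a rule is written. Under graded, assumed mechanisms with 11% to 20% incomplete, the shift from a true 0.40 is 0.01 to 0.02 if loss follows one score and at most 0.10 if it follows both, against an interval half-width of about 0.25 at n = 45. Only a sharp loss of the patients worst on both scores would rival the sampling error, and the documents give no reason to expect that in a single one-hour visit. The fear of unrecoverable scores presumes that completed parts go unentered, which Section 11.2 does not say. Section 12 already treats a positive result as one to be confirmed in a larger multicentre study. No change follows. The judgement would be less comfortable if a substantial share of patients failed to finish and those lost were clearly the worst on both measures; that would show in the counts and reasons an ordinary report gives.
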